## **Additional Laboratory Assessments**

# **Safety**

- Serum calcitonin (pg/mL)
- Serum amylase (presented in both SI unit: μkat/L and conventional: U/L) and lipase (U/L)
- Coagulation parameters (prothrombin time [s], activated partial thromboplastin time [s], and international normalized ratio [INR] [ratio])
- MELD score (composite of INR, sodium, bilirubin, and creatinine)
- eGFR (mL/min/1.73 m^2) (Inker et al 2021)

Laboratory test results for hematology, coagulation, and clinical chemistry quantitative parameters below the lower limit of quantification for which the exact value cannot be determined, will be replaced with the  $0.99 \times LLOQ$  value. Similarly, laboratory test results above the upper limit of quantification (ULOQ) for which the exact value cannot be determined, will be replaced with  $1.01 \times the ULOQ$  value.

After the LLOQ/ULOQ replacement, change from baseline to each post-baseline visit for hematology, coagulation, clinical chemistry, MELD, and urinalysis quantitative parameters is defined as the post-baseline visit value minus the baseline value.

After the LLOQ/ULOQ replacement, hematology, coagulation, and clinical chemistry and quantitative parameters are also classified as normal (if value is within normal reference range), low (if value is below the normal reference range), and high (if value is above the normal reference range) based on the reference range indicator. Tables will utilize the LLOQ/ULOQ replacement. However, listings will display the original LLOQ/ULOQ inequality (eg, "< x" and "> x").

# Potential Hy's Law

AST or ALT  $\geq$  3 × Upper Limit of Normal (ULN) together with TBL  $\geq$  2× ULN at any point during the study following the start of study intervention irrespective of an increase in ALP. Potential Hy's Law cases are determined without regard to the baseline value. The elevation in transaminases must precede or be coincident with (ie, on the same day) the elevation in TBL, but there is no specified timeframe within which the elevation in transaminases and TBL must occur.

# 4.5.3.2 Presentations

Tables, graphs, and listings for laboratory data will be based on the on-study data only in the safety population and presented for each treatment group.

Laboratory test results for continuous clinical laboratory parameters will be summarized with n, mean, SD, median, minimum and maximum by treatment and analysis visit, and for change from baseline. Categorical parameters will be summarized by number and percentage of participants in each category by treatment and analysis visit. A frequency table will present number of participants reporting at least 1 treatment-emergent abnormality in chemistry, hematology, or coagulation clinical safety laboratory tests by highest category (Level 1 to 3, where Level 3 is the most extreme; refer to Appendix A for ranges). Low and high abnormalities for the same laboratory parameter will be summarized separately. Shifts from baseline to maximum value during the on-study period will be presented for urinalysis qualitative parameters.

Potential Hy's Law cases will be summarized by treatment and listed, and will be displayed for both the on-treatment and on-study periods. Maximum on-treatment ALT, AST, and TBL will be analyzed using categories described below and using baseline as defined in this document.

Participants with normal/near normal ALT ( $\leq 1.5 \times \text{ULN}$ ) at baseline:

- ALT < 3 × ULN and bilirubin not elevated (Non-Gilbert: Not elevated = total bilirubin < 2 × ULN. Gilbert: Not Elevated = direct bilirubin < 2 × baseline and INR  $\leq$  1.5)
- ALT <  $3 \times$  ULN and bilirubin elevated (Non-Gilbert: Elevated = total bilirubin  $\geq 2 \times$  ULN. Gilbert: Elevated = direct bilirubin  $\geq 2 \times$  baseline or INR > 1.5)
- ALT  $> 3 \times ULN$  and bilirubin not elevated
- ALT  $\geq$  3 × ULN and bilirubin elevated
- ALT  $> 5 \times ULN$  and bilirubin not elevated
- ALT  $\geq$  5 × ULN and bilirubin elevated
- ALT  $> 8 \times ULN$  and bilirubin not elevated
- ALT > 8 × ULN and bilirubin elevated
- (repeat same categories with AST instead of ALT)

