Absolute change from baseline values over time Abnormality at least once on treatment Laboratory parameters include Clinical Chemistry (including MELD score) and Hematology parameters as well as urinalysis. A complete list of parameters is presented in Section 8.2.5. Assessments cover: Observed value Absolute change from baseline values over time Abnormality/Clinically significant abnormality in laboratory parameters at least once on treatment Treatment-emergent increase in hematuria, proteinuria, and glucose in urinalysis defined as change from negative/trace at baseline to ++, +++, or ++++ at any visit after baseline or an increase of at least ++ Electrocardiogram measurements include heart rate, RR, PR, QRS, and QT intervals. Derived variables cover OTcF. Assessments cover: Observed value Absolute change from baseline values over time ECG parameters fulfilling potentially clinically significant criteria (PCS) at any time during treatment, including ORS duration > 118 ms, PR interval > 210 ms, RR < 600 ms (resting heart rate > 100 bpm), and RR > 1330 ms (resting heart rate < 45 bpm) QTcF exceeding 450, 480, and 500 ms at any time during treatment Change in QTcF at any time during treatment as compared to baseline exceeding 30 ms and 60 ms To assess the immunogenicity of Incidence of ADAs to cotadutide and titer during cotadutide treatment and follow-up **Exploratory** To determine whether cotadutide is Proportion of participants with resolution of NASH superior to placebo on resolution of NASH without worsening of liver fibrosis based on biopsy at without worsening of liver fibrosis in Week 48 participants with non-cirrhotic NASH with fibrosis Proportion of participants with improvement of liver To assess the effect of cotadutide versus placebo on improvement in fibrosis by at fibrosis by at least one stage without worsening of least one stage without worsening of NASH based on biopsy at Week 48 NASH To assess the effect of cotadutide versus Proportion of participants with both resolution of NASH and improvement in fibrosis by at least one placebo on resolution of NASH and improvement in fibrosis stage based on biopsy at Week 48

•	To assess the effect of cotadutide versus placebo on improvement in fibrosis by at least one stage	Proportion of participants with improvement in fibrosis by at least one stage based on biopsy at Week 48

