# 3.3.1.2 Definition of On-study and On-treatment

All adverse events (AEs) with start date on or after the date of first treatment will be considered on-study. On-treatment AEs are those occurring within the on-study period and within + 7 days of treatment discontinuation. All AEs leading to discontinuation of IP will be considered on-treatment.

On-study assessments (eg, vital signs, clinical laboratory tests, ECG) are defined as those occurring after the date and time (if available) of administration of the first dose of IP. On-

treatment assessments are defined as those occurring within the on-study period and on or before the date of administration of the last dose of IP with the following windows following treatment discontinuation:

- Fasting plasma glucose (FPG): +1 day from treatment discontinuation.
- Biopsy, liver tests (alanine aminotransferase [ALT], aspartate aminotransferase [AST], total bilirubin [TBL], and alkaline phosphatase [ALP]), and disease-specific biomarkers: + 30 days from treatment discontinuation.
- All other efficacy and safety: +7 days from treatment discontinuation.

Assessments other than AEs recorded on the day of first treatment and with time unavailable for the assessment or for the first dose, will be considered to be not in the on-study/on-treatment periods. For listings of AEs, analysis phase will be indicated as on-treatment if the AE starts within the on-treatment period, as 'pre-treatment' if it starts prior to the on-treatment period, and as 'post-treatment' if it starts after the on-treatment period.

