#### Assessments cover:

- Observed value
- Absolute change from baseline values over time
- Abnormality/clinically significant abnormality in laboratory parameters at least once on treatment
- Treatment-emergent increase in hematuria, proteinuria, and glucose in urinalysis defined as change from negative/trace at baseline to ++, +++, or ++++ at any visit after baseline or an increase of at least ++

Electrocardiogram measurements include heart rate, RR, PR, QRS, and QT intervals. Derived variables cover OTcF.

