#### 4.5.4.2 **Presentations**

Vital sign tables, graphs, and listings will be based on the on-treatment data only in the safety population and presented for each treatment group.

Vital sign results will be summarized with n, mean, SD, median, minimum, and maximum by treatment, and analysis visit and for change from baseline. A frequency table will present number of participants reporting at least 1 treatment-emergent abnormality (result outside of reference range). Low and high abnormalities for the same vital sign will be summarized separately. Observed values and change from baseline in SBP and heart rate measurements will be also presented in figures with mean and standard error of the mean.

All vital sign data will be listed. The listing will include reference ranges and classification of vital signs as normal, low, and high.

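### The primary laboratory abnormality endpoint is defined on treatment, but the SAP's Level 1 to 3 abnormality table uses on-study data, so off-drug samples are counted and the endpoint as worded is not tabulated

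*SAP*

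**What the plan says.** Protocol Table 8 (Section 3.1) lists among the primary safety endpoints "Abnormality/Clinically significant abnormality in laboratory parameters at least once on treatment". SAP 4.2.1 repeats it: "Abnormality/clinically significant abnormality in laboratory parameters at least once on treatment".

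SAP 3.3.1.2 separates two periods. On-study assessments are everything after the first dose, with no upper limit. On-treatment assessments end at the last dose plus a margin. That margin is 1 day for fasting plasma glucose. For ALT, AST, total bilirubin and ALP it is "30 days from treatment discontinuation". The rule for the rest is "All other efficacy and safety: +7 days from treatment discontinuation".

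SAP 4.5.3.2 opens with "Tables, graphs, and listings for laboratory data will be based on the on-study data only". It then specifies a frequency table of participants with at least one treatment-emergent chemistry, hematology or coagulation abnormality, by highest level, using the Appendix A cutoffs. SAP 4.5 calls a laboratory result treatment-emergent if it was collected after the first dose and is more extreme than baseline. It sets no end to that period, and for random glucose it waives the baseline comparison.

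The parallel vital signs outputs (SAP 4.5.4.2) are "based on the on-treatment data only in the safety population", and SAP 4.5.5.2 restricts ECG outputs in the same way.

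**The concern.** Safety is the primary objective and will be reported descriptively, so the counts in these tables are the primary result. The endpoint asks how many participants had a laboratory abnormality while on drug. The planned table answers how many had one at any time after the first dose, including about four weeks after the last injection. No on-treatment version of the Level 1 to 3 table is specified. SAP Section 2 declares no departure from the protocol other than the per-protocol set, so a reader of the study report would have no reason to expect a difference.

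Random glucose shows the problem most clearly. Fasting is confirmed at Visit 2, Week 48 and early discontinuation, but not at follow-up, so a glucose value at follow-up is a random one. With no planned baseline, any such value of 200 mg/dL or more is a Level 2 abnormality, although dosing has stopped. Participants with type 2 diabetes may enter with HbA1c up to 10.5%, so such values are not far-fetched.

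**Working it through.** The plan gives no figure to reproduce. The check compares definitions with the visit schedule and then sizes the result.

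**1. Endpoint against data period**

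| Domain | Period in the endpoint | Period in the planned abnormality table |
|---|---|---|
| Laboratory, Appendix A | on treatment | on-study |
| Vital signs | on treatment | on-treatment |
| ECG criteria | during treatment | on-treatment |

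The vital signs table is also labelled treatment-emergent, yet it is limited to on-treatment data. The label therefore does not set the period.

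**2. Follow-up timing against the windows**
- Follow-up is 4 weeks ± 5 days after end of treatment or early discontinuation (protocol Table 4): 28 − 5 = 23 to 28 + 5 = 33 days.
- Against +7 days, every such draw is outside the window when dosing ends near that visit.
- Against +30 days (ALT, AST, total bilirubin, ALP), most are inside. ALP is the only one of these four in Appendix A, so it is little affected.
- With Week 48 on its target day, follow-up falls on study day 337 + 28 = 365, range 360 to 370. This is inside the Week 52 window of SAP Table 4 (days 352 to 385).

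**3. Share of scheduled samples off drug, completer**
- Chemistry and hematology: Weeks 4, 8, 12, 16, 20, 24, 32 and 48 give 8 on treatment, plus follow-up. 1/9 = 11%.
- Random glucose: Week 48 is a fasting visit, so 7 on treatment plus follow-up. 1/8 = 12.5%.
- Amylase, lipase and coagulation: Weeks 24, 32 and 48 give 3, plus follow-up. 1/4 = 25%.

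The last figure assumes that the table reads every on-study record. SAP Table 5 has no Week 52 window, and its Week 48 window (days 281 to 378) takes in both draws. If the one-record-per-window rule of SAP 3.3.3 also governs this table, the Week 48 draw is nearer to day 337 and displaces the follow-up draw. The SAP does not say which applies. Chemistry and hematology keep the follow-up value either way.

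**4. Early stopper, last dose at Week 8**
- On drug: Weeks 4 and 8.
- Required off drug: one draw about 28 days later (Week 12, or follow-up after early discontinuation). Protocol 7.1 does not require safety samples more than 30 days after stopping, except to follow abnormalities or adverse events. 1/3 = 33%.

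**5. Illustrative effect on the proportion with at least one abnormality**

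Assumptions not in the documents: independent samples, a per-sample probability q of abnormality of 1% to 10%, and all visits attended. With k on-treatment samples the proportion is 1 − (1 − q)^k. One more sample adds q(1 − q)^k.

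| k | q | k samples | k + 1 samples | Added (points) |
|---|---|---|---|---|
| 8 | 1% | 7.7% | 8.6% | 0.9 |
| 8 | 10% | 57.0% | 61.3% | 4.3 |
| 3 | 1% | 2.97% | 3.94% | 0.97 |
| 3 | 10% | 27.1% | 34.4% | 7.3 |

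**6. One participant**

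About 55 randomized 2:1:2:1 gives 55 × 2/6 ≈ 18 per active dose. One extra flagged participant moves that rate by 1/18 = 5.6 points. This is a unit of scale, not an estimate of bias.

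**The case against.** The strongest defense is that the SAP follows the protocol's own analysis section. Protocol 9.4.3 plans a table of treatment-emergent laboratory changes, and SAP 4.5 defines that term. On-study reporting is also the SAP's default for adverse events (4.5.2.2), and it catches delayed findings. The on-study table contains every on-treatment abnormality, chemistry and hematology have their own Week 52 column, and all values are listed. The rule is the same in every arm, and nothing is formally tested.

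This narrows the point but does not remove it. Protocol 9.4.3 does not withdraw the on-treatment condition in Table 8, and a count over a wider period is not the count that the endpoint asks for.

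Several stronger readings may tempt a reader, and the documents do not support them:
- **Rebound in ALT after stopping would inflate the table.** ALT, AST and total bilirubin are not in Appendix A. Their maximum-value categories and the eDISH and cholestatic plots use on-treatment data, and potential Hy's Law is shown for both periods.
- **A return to baseline would be flagged.** It would not, because the result must be more extreme than baseline. Random glucose is the planned exception, along with any parameter whose baseline is missing.
- **Off-drug values are presented as on-treatment abnormalities.** They are labelled treatment-emergent.
- **The whole laboratory endpoint is missing.** Observed values and changes over time carry no on-treatment condition, and the urinalysis component refers to any visit after baseline.
- **Half of an early stopper's samples are off drug.** Required draws give about one third at Week 8. Later draws taken to follow an abnormality are selected for being abnormal, but many of those participants will already have been counted.

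**Conclusion.** The mismatch stands for one component of the primary laboratory endpoint: abnormality at least once on treatment, for the non-liver chemistry, hematology and coagulation parameters in Appendix A. The planned table counts off-drug samples, and no planned table gives the on-treatment count.

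The size is modest. One of 9 scheduled chemistry and hematology samples in a completer is off drug, and 1 of 4 for amylase, lipase and coagulation. These shares assume that dosing ends near Week 48 and all visits are attended; the second also assumes that every record is read. Under the assumed q of 1% to 10%, one extra sample adds about 0.9 to 7.3 points to a parameter's abnormality rate. No type I error or power is involved. A reader might infer that the excess would fall mainly in the cotadutide arms. That is plausible for a glucose-lowering drug, but the documents give no figure that shows it, and the rule applies equally to placebo.

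**What to change.** - Produce the Level 1 to 3 abnormality table on on-treatment data, using the SAP 3.3.1.2 windows, as the analysis of the endpoint.
- Keep the on-study version as a supportive table, so that delayed findings remain visible.
- Reword the opening sentence of SAP 4.5.3.2 to name the period for each output. As written, it conflicts with the on-treatment liver outputs later in the same section.
- In the same sentence, say whether the table reads every record or one per visit window.

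The cost is one rerun of a planned table with a period flag that the SAP already defines, plus the rewording. No new data are needed.

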Baseline pretreatment ALT is derived from the average of the last ALT measurement prior to randomization and the randomization visit (V2) based on central laboratory assessments. Elevated baseline is defined as ALT > 1.5 × ULN.

ALP, alkaline phosphatase; ALT, alanine aminotransferase; AST, aspartate aminotransferase; DILI, drug-induced liver injury; INR, international normalized ratio; TBL, total bilirubin; ULN, upper limit of normal

Figure 3 Stopping Criteria and Dose Adaptations for Possible Hepatocellular DILI in Participants with Elevated ALT at Baseline

Liver-related symptoms include: severe fatigue, nausea, vomiting, right upper quadrant pain.

Baseline pretreatment ALT is derived from the average of the last ALT measurement prior to randomization and the randomization visit (V2) based on central laboratory assessments. Elevated baseline is defined as ALT  $> 1.5 \times ULN$ . If on treatment a participant has 2 or more consecutive ALT values at scheduled visits based on central laboratory assessments, each less than 50% of the baseline ALT and they are within 40% of each other (with percentage calculated based on the larger value as the denominator), then a new baseline should be set to be the minimum of the latest consecutive pair of values that are "stable" (ie, within 40% of each other).

ALP, alkaline phosphatase; ALT, alanine aminotransferase; AST, aspartate aminotransferase; DILI, drug-induced liver injury; INR, international normalized ratio; TBL, total bilirubin; ULN, upper limit of normal

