Safety Analysis 10NOV2022		4.5.1.1 Analysis of "actual exposure", which was included in addition to "exposure", was removed.	Yes	Remove redundancy
Safety Analysis 10NOV2022		4.5.2.1 Gallbladder-related disease added to list of AESIs.	Yes	Align with CSP amendment
Safety Analysis 10NOV2022		4.5.2.1 Definition of MACE added.	Yes	Clarification
Safety Analysis	10NOV2022	4.5.2.2 Description of analysis of adjudicated events added.	Yes	Clarification
Safety Analysis	10NOV2022	4.5.3.1 Specified laboratory parameters to be presented in conventional as well as SI units.	Yes	Clarification

CATEGORY Change refers to:	Date	Description of change	In line with CSP?	Rationale
Safety Analysis	10NOV2022	4.5.3.1 Updated list of safety laboratory variables to remove screening labs that will not be included in CSR analyses.	Yes	Clarification
Safety Analysis	10NOV2022	4.5.3.1 Lab results below the lower limit of quantitation will be imputed as 0.99*LLOQ rather than LLOQ, and results above the upper limit will be imputed as 1.01*ULOQ instead of ULOQ.	Yes	Update made based on issues encountered for other studies
Safety Analysis	10NOV2022	4.5.3.1, 4.5.3.2 AST, ALT, and TBL shift tables were replaced with an analysis more closely aligned with the potential hepatocellular DILI algorithm described in the CSP.	Yes	More closely align analysis with CSP
Safety Analysis 10NOV2022		4.5.3.2 eDISH plots will use maximum of ALT or AST rather than maximum of ALT. In addition, cholestatic DILI screening plots were added (TBL vs ALP).	Yes	Clarification
Safety Analysis 10NOV2022		4.5.3.2, Appendix A. Ranges added for categorical (outlier) analysis of chemistry, hematology, and coagulation results.	Yes	Clarification
Safety Analysis	10NOV2022	4.5.4.2 MMRM analysis, which is included as an exploratory efficacy analysis, was removed from this section.	Yes	Correction/ Clarification
Interim Analysis	10NOV2022	5 Section 5 renamed since there will no longer be a planned interim analysis of efficacy.	Yes	Align with CSP amendment
General 25OCT2023		The SAP was updated to reflect changes introduced in the protocol amendment (v3.0).	Yes	Align with CSP amendment
Efficacy Analysis 17MAY2024		3.2, 4.1.2.1 Update to definition of the per protocol set. Difference from CSP noted in Section 2	No	Response to quality incident
General 17MAY2024		3.3.1.1, 3.3.2, 4.5 Details for distinguishing random glucose vs fasting glucose in the analysis		Response to dry run findings

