# **3.3.1** General Study Level Definitions

#### 3.3.1.1 Definition of Baseline

Baseline biopsy specimen refers to either historical biopsies or on-study biopsies obtained during the screening period. Central pathology review of the eligibility read will occur upon baseline biopsy specimen receipt and processing at the histopathology vendor. Central pathology review results will support patient eligibility and enrollment. This is referred to as the eligibility read and will serve as the baseline for histology analyses.

For continuous endpoints, the baseline value for statistical analysis is the last non-missing value on or prior to date and time (if available) of administration of the first dose of IP. If multiple measurements occur on the same day, the last non-missing value on or prior to the time of first dosing of study drug will be considered as the baseline value. If these multiple measurements occur at the same time or the time is not available, the average of these measurements (for continuous data) will be considered as the baseline value. For electrocardiogram (ECG) parameters, the mean of the last set of triplicate measures prior to treatment is baseline.

For categorical endpoints, the last available record on or prior to the date of the first dose of study drug will be selected. If there are ties in terms of proximity to first dose, the value with the lowest severity will be selected (eg, normal will be selected over abnormal for safety ECG findings and '+' will be selected over '++' for urinalysis findings).

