# Participants with elevated ALT ( $> 1.5 \times ULN$ ) at baseline

- ALT < 2 × baseline and bilirubin not elevated (Non-Gilbert: Not elevated = total bilirubin < 2 × ULN. Gilbert: Not Elevated = direct bilirubin < 2 × baseline and INR  $\leq$  1.5)
- ALT < 2 × baseline and bilirubin elevated (Non-Gilbert: Elevated = total bilirubin  $\geq$  2 × ULN. Gilbert: Elevated = direct bilirubin  $\geq$  2 × baseline or INR > 1.5)
- ALT  $> 2 \times$  baseline and bilirubin not elevated
- ALT  $> 2 \times$  baseline and bilirubin elevated
- ALT  $> 3 \times$  baseline and bilirubin not elevated
- ALT  $> 3 \times$  baseline and bilirubin elevated
- ALT  $> 5 \times$  baseline and bilirubin not elevated
- ALT  $\geq$  5 × baseline and bilirubin elevated
- (repeat same categories with AST instead of ALT)

Evaluation of drug-induced serious hepatotoxicity (eDISH) plots of the maximum ontreatment (peak) TBL versus peak ALT or AST will be provided by treatment. Additionally, a cholestatic DILI screening plot will be provided plotting peak on-treatment TBL versus peak on-treatment ALP.

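### Should the SAP's peak-ALT table use the protocol's averaged and resettable DILI baseline instead of one fixed pre-dose value?

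*SAP*

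**What the plan says.** The hepatic category table in SAP 4.5.3.2 is introduced by "Maximum on-treatment ALT, AST, and TBL will be analyzed using categories described below and using baseline as defined in this document". Under SAP 3.3.1.1, "the baseline value for statistical analysis is the last non-missing value on or prior to date and time" of first dosing. Values from different visits are not averaged, and the figure does not move after dosing starts. Participants with baseline ALT above 1.5 × ULN are classified by multiples of that value, with limits at 2, 3 and 5; the lowest row begins "ALT < 2 × baseline and bilirubin not elevated". The others are classified by multiples of ULN, with limits at 3, 5 and 8.

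The footnotes to Figures 2 and 3 in protocol 8.3.10 define a different reference. The pre-treatment ALT is "derived from the average of the last ALT measurement prior to randomization and the randomization visit (V2"). The Figure 3 footnote, for participants with elevated baseline, adds a reset. After at least two consecutive scheduled values that are each below half the baseline and within 40% of one another, "then a new baseline should be set to be the minimum of the latest consecutive pair of values". The same section presents the algorithm as the means of monitoring and managing possible DILI.

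The two are linked by the SAP Amendment History, where the former AST, ALT and bilirubin shift tables were "replaced with an analysis more closely aligned with the potential hepatocellular DILI algorithm described in the CSP".

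**The concern.** The table takes over the algorithm's 1.5 × ULN split and expresses results as multiples of baseline, yet it measures them from a different starting point and does not spell out the difference. Safety is the primary objective, and this is the only planned hepatic table that sets a participant's peak ALT against that participant's own level. For the Hy's Law summary, "Potential Hy's Law cases are determined without regard to the baseline value"; the eDISH plots show peaks; and SAP Appendix A, Table A1, has no ALT, AST or bilirubin rows.

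Protocol 2.1 reports dose-dependent falls in liver enzymes on cotadutide, so resets may well be more frequent in the active arms. A rise from a drug-lowered level could then sit in the lowest row, and the table would be least sensitive where sensitivity matters most.

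**Working it through.** The documents give no figure to reproduce here, so the check is algebra on the two definitions. Only the footnotes of Figures 2 and 3 were available in the text reviewed, so the figures' own thresholds are not used.

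**Notation.** S is the SAP baseline (last pre-dose value). P is the protocol baseline (mean of two values). R is the reset baseline, so R < 0.5P. A k-fold rise after reset gives ALT = kR.

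**When the rise falls in the lowest row.** It does so when kR < 2S, that is, when k < 2S/R. Because R < 0.5P, 2S/R is greater than 4S/P.
- If S = P, every rise below 4-fold is in the lowest row.
- If S/P = 0.7, the guaranteed limit is 4 × 0.7 = 2.8. If S/P = 1.3, it is 4 × 1.3 = 5.2.
- Counterexample to a flat 4-fold rule: screening 3.0 and Visit 2 2.0 × ULN give P = 2.5 and S = 2.0. A reset to 1.225 (below 1.25) followed by a 3.5-fold rise gives 3.5 × 1.225 = 4.29 × ULN. The ratio is 4.29/2.0 = 2.14, which is above the lowest row.
- The table takes the maximum over all on-treatment values, so a higher value before the reset sets the row whatever happens later.

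A simulation assumed within-person CVs of 10%, 20% and 30%, R uniform on 0.25P to 0.5P, and rises uniform on 2- to 4-fold. It put 99.5%, 98.1% and 96.2% of such rises in the lowest row. With R between 0.45P and 0.5P and rises of 3- to 4-fold, the shares were about 95%, 87% and 80%. Earlier peaks were not modelled. The mechanism is therefore common once a reset has occurred; how often resets occur is unknown.

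**What the reset ratio would show instead.** Take S = P = 120 with a stable pair of 55 and 50. Both are below 60, and (55 − 50)/55 = 9%, so R = 50.

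| Later peak | Peak / 120 | Peak / 50 |
|---|---|---|
| 120 | 1.00 | 2.40 |
| 200 | 1.67 | 4.00 |
| 250 | 2.08 | 5.00 |

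The first line matters most for choosing a baseline. Going back to entry level is 2.4-fold on the reset scale, with no excess over the pre-treatment state. Off-drug values can produce exactly this. SAP 3.3.1.2 counts liver tests as on-treatment up to 30 days after stopping, and the follow-up visit falls 28 ± 5, or 23 to 33, days after the end-of-treatment visit. A washout return to entry level can therefore be the on-treatment maximum.

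**The 1.5 × ULN split.** Screening 1.9 and Visit 2 1.3 × ULN give P = 1.6 (elevated) and S = 1.3 (near normal). The SAP limits are then 3, 5 and 8 × ULN. With the mean they would be 2 × 1.6 = 3.2, 3 × 1.6 = 4.8 and 5 × 1.6 = 8.0 × ULN. They move by at most 0.2 × ULN, and the lowest becomes less sensitive. At the boundary itself the elevated-group limits are 3.0, 4.5 and 7.5 × ULN against 3, 5 and 8.

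**Width of the lowest row.** Its upper limit is 2S, which starts at 2 × 1.5 = 3 × ULN. The documents give no upper bound: exclusion criterion 25(a) limits ALT at screening, whereas S is normally the Visit 2 value. A wide lowest row is in any case a feature of every multiple-of-baseline table, with or without a reset.

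**Numbers.** About 55 randomized participants at 2:1:2:1 give 55 × 4/6 ≈ 37 on cotadutide and 55 × 2/6 ≈ 18 on placebo. Only the elevated-baseline subset can have a reset.

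**The case for a change.** The strongest case for a change is that it would be cheap. ALT is scheduled at eight post-baseline visits during treatment (Weeks 4, 8, 12, 16, 20, 24, 32 and 48), giving seven consecutive pairs, so resets could be derived without new data. One could keep the fixed-baseline table, use the two-value mean for ALT, and add a descriptive panel of resets and later peaks with returns to entry level marked. Since the table was introduced for alignment, a reader might reasonably assume that its baseline is the algorithm's.

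Part of this stands. The SAP does not say that its baseline differs from the algorithm's, and a reader comparing a managed case with its table row could be puzzled. The rest is weaker. Closer alignment than the shift tables is not identity, and the laboratory analyses in protocol 9.4.3 prescribe neither this table nor a DILI baseline, so no planned analysis is contradicted. Even that proposal retains the fixed-baseline table for comparing arms. The extra panel would have a denominator formed after randomization and influenced by treatment, and so could not support a comparison between arms. An averaged baseline for ALT alone would differ from AST in the same table and from ALT elsewhere in the SAP, because the protocol's averaging and reset cover ALT only.

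Nor are such rises lost. By-visit summaries give observed ALT and change from baseline with maxima, peaks appear in the eDISH plots, all scheduled and unscheduled assessments are listed (SAP 3.3.3), and suspected DILI is adjudicated and tabulated. At about 55 participants the listings can be read person by person.

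**Conclusion.** No change to the plan follows. The table is correct as labelled. It shows how far peak ALT exceeded the level before treatment, while the protocol's algorithm asks how far a value exceeds the participant's most recent stable level, for individual case handling. Using a fixed value for the first question and a moving one for the second is a fair trade-off.

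The masking of post-reset rises below 4-fold is genuine but conditional. It requires elevated baseline ALT, a reset, S = P (otherwise the limit is 4S/P) and no higher earlier on-treatment value. How many participants meet these conditions cannot be derived: the documents give neither the frequency of resets nor the within-person variability of ALT. The simulated percentages rest on assumed values for the latter. The undescribed difference is one that analysts can cover with a table footnote when producing the output. Adjudicated DILI, adverse events of special interest, potential Hy's Law, eDISH plots and listings are the same under either baseline.
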